### 3.14.4.2. Missed Visits

Visits will be scheduled using target visit windows, as detailed in the Study Manual. When a subject cannot return to the clinic within her visit window, missed procedures will be performed at her next clinic visit.

### 3.14.4.3. Lost to Follow-up

If a subject fails to appear for a scheduled visit, at least 3 attempts to contact the subject will be made. One additional attempt to contact the subject will be made after each subsequent missed study visit. These attempts will be documented in the subject's study file. If the subject does not return for the scheduled appointment, the subject will be considered "presumed lost to follow-up". The subject's file will remain open until study closeout. If the subject does not return to the study before the study is closed, the Final form will be completed at the end of the study (see Section 11.4 for definition). The form will indicate that the subject was lost to follow-up. The final "lost to follow-up" designation cannot be made for any subject until the closing date of the study.

### 3.14.5. Unscheduled Visits

An unscheduled visit may be performed at any time during the study at the subject's request or as deemed necessary by the investigator. The date and reason for the unscheduled visit will be recorded on the CRF as well as any other data obtained, if applicable (eg, adverse events, concomitant medications and treatments, and results from procedures or tests).

Procedures performed during unscheduled visits include the following:

- concomitant medication inquiry
- vital signs measurements (BP [systolic/diastolic], pulse, and respiration)
- adverse event inquiry

Other procedures may be performed at the discretion of the investigator.

# 4. SELECTION AND WITHDRAWAL OF SUBJECTS

Prospective waivers (exceptions) from study eligibility criteria to allow subjects to enter a study are not granted by Teva (see Section 10.1.2).

## 4.1. Subject Inclusion Criteria

Subjects may be included in the study if they meet all of the following criteria:

- a. has regular menstrual cycle (24 to 35 days)
- b. has confirmed ovulatory cycle during the pretreatment phase (serum progesterone  $\geq$ 4.7 ng/mL in 2 consecutive samples)
- c. is at low risk of pregnancy (ie, sterilized, in exclusively same-sex partnership, in monogamous relationship with vasectomized partner, or using non-hormonal IUD)
- d. is in good general health as determined by a medical history
- e. 18 to 40 years of age, inclusive
- f. willing to provide informed consent and follow all study requirements
- g. is not pregnant and does not have desire to become pregnant in the subsequent 36 months
- h. has a BMI of 18 to 35, inclusive (unless included in subset of subjects with extreme obesity (BMI ≥40), 2 in each dose-range finding group from a single investigational center, in Part 2)
- i. has hemoglobin  $\geq 10.5$  g/L
- j. has had a normal mammogram within the last year (for Part 1 only)

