# 1.4.1. Benefits of TV-46046

All potential subjects will be tested for anemia to meet inclusion criterion "i" before being enrolled in the study. There will be no other direct benefit to the subjects. The results of this study may facilitate the development of a new longer-acting injectable contraceptive.

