### **Menstrual Changes**

Most women using Depo-Provera CI or Depo-subQ 104 experience disruption of menstrual bleeding patterns. Altered menstrual bleeding patterns include amenorrhea, irregular or unpredictable bleeding or spotting, prolonged spotting or bleeding, and heavy bleeding. As women continue using Depo-Provera CI or Depo-subQ 104, fewer experience irregular menstrual bleeding and more experience amenorrhea. In 3 contraception trials, 39.0% of women experienced amenorrhea during month 6, and 56.5% experienced amenorrhea during month 12 (Depo-subQ 104 US Prescribing Information 2016). The effect on bleeding pattern of a single subcutaneous administration of TV-46046 has not been clinically tested. Women with

unexplained vaginal bleeding or anemia (hemoglobin <10.5 g/dL) will not be eligible for the study. Changes in menstrual bleeding patterns and its acceptability will be evaluated at specified study visits. For details, see the Study Procedures and Assessments table (Table 1).

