### 3.14.3. Procedures During Study Drug Treatment

### 3.14.3.1. Enrollment (Injection) Visit (Day 0)

The enrollment visit should take place during the first 5 days of menses. During this visit, a urine pregnancy test will be performed. Participants with hemoglobin  $\geq 10.5$  g/dL measured at screening, confirmed ovulation and negative pregnancy test will be enrolled in the study. Medications that the subjects used over the last 30 days will be documented as concomitant medications; vital signs (BP [systolic/diastolic], pulse, and respiration), and body weight will be measured and blood samples will be collected for serum MPA, serum progesterone, and estradiol before the study drug injection.

Part 1 is open-label; therefore, subjects will be assigned without randomization. The study staff allocating the study drug assignments in Part 2 will open the next sequential randomization envelope, document treatment assignment in a secure log, store the opened envelope, and communicate the assigned treatment arm to the pharmacy and/or study staff preparing and administering the injection (unless s/he is the one administering the injection).

The Part 2 investigational center staff who assigns the study drug treatment, and study staff providing the injection, will not be blinded but they will keep the subject and the rest of the investigational center staff unaware of the study drug treatment assignment. The study staff member will prepare the assigned study drug for injection according to the dilution procedures, and, unless s/he is the one administering the injection, pass it to the study staff who will inject the study drug subcutaneously in the fatty tissue over the abdomen while shielding the study drug injection from the subject's sight, as described in Section 5.1. After the injection the unblinded study staff will provide feedback on the ease of the injection administration. On the injection day the injection site will be examined for ISRs twice: within 10 minutes after the injection (by the un-blinded provider) who performed the injection; and within 1st hour after the injection (between 10 and 60 minutes) (by the blinded investigational center staff). The subject will be interviewed for acceptability of the study injection by the blinded investigational center staff. Before leaving the investigational center during the injection visit, each subject will receive the schedule of their follow-up visits.

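### Inclusion criterion i prints the haemoglobin threshold in g/L, ten times lower than the g/dL threshold in Sections 1.4.2 and 3.14.3.1

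*Protocol*

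**What the plan says.** The haemoglobin threshold for entry is stated in four places in the protocol.

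- Synopsis, Inclusion Criteria, item i, and Section 4.1, item i: the woman "has hemoglobin $\geq 10.5$ g/L".
- Section 1.4.2, Menstrual Changes: women with "unexplained vaginal bleeding or anemia (hemoglobin <10.5 g/dL) will not be eligible for the" study.
- Section 3.14.3.1, Enrollment (Injection) Visit: "Participants with hemoglobin $\geq 10.5$ g/dL measured at screening" are enrolled, provided that ovulation is confirmed and the pregnancy test is negative.

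Section 1.4.1 ties the criterion to its purpose: "All potential subjects will be tested for anemia to meet inclusion criterion 'i' before being enrolled in the study". Section 4 opens by ruling out exceptions: "Prospective waivers (exceptions) from study eligibility criteria to allow subjects to enter a study are not granted by Teva".

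The exclusion list in Section 4.2 has no anaemia item, so criterion i is the only entry criterion on haemoglobin.

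**The concern.** The same number appears with two units that differ tenfold. This is a decision threshold that a site applies to each candidate, not background text. Section 1.4.2 sets it among the menstrual effects of the drug class, which include heavy bleeding, so it serves as a safety screen.

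Two uses of the threshold are affected. First, under Section 3.14.2, women who meet the inclusion and exclusion criteria at screening go on to the pretreatment blood draws, up to 6 visits according to Section 3.14. That decision refers to the criteria list, where the unit is g/L. Second, protocol Section 8.4.1 and SAP Section 5.8 tabulate violations of study entry criteria. Whoever classifies a low haemoglobin at entry would reach different answers from Section 4.1 and from Sections 1.4.2 and 3.14.3.1.

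Sections 3.13 and 7.4 have haemoglobin measured at local laboratories, and the synopsis plans up to 5 centres in three countries. The documents do not say which unit those laboratories report, so a single stated unit matters.

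**Working it through.** **Inputs**

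- Criterion i (synopsis and Section 4.1): at least 10.5 g/L.
- Section 1.4.2: below 10.5 g/dL is not eligible.
- Section 3.14.3.1: at least 10.5 g/dL is required to be enrolled.
- Conversion: 1 g/dL = 10 g/L.

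**Step 1: put both thresholds in the same unit**

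- Criterion i as printed: 10.5 g/L ÷ 10 = 1.05 g/dL.
- Sections 1.4.2 and 3.14.3.1: 10.5 g/dL × 10 = 105 g/L.
- Ratio: 10.5 ÷ 105 = 0.1, a factor of exactly 10.

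Sections 1.4.2 and 3.14.3.1 agree with each other: one excludes below 10.5 g/dL and the other admits at or above it. The synopsis and Section 4.1 also agree with each other. The conflict is between the two pairs.

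**Step 2: apply both rules to example values**

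| Haemoglobin (g/dL) | Meets criterion i as printed | Meets Section 3.14.3.1 |
|---|---|---|
| 0.9 | no | no |
| 1.05 | yes | no |
| 5 | yes | no |
| 8 | yes | no |
| 10.4 | yes | no |
| 10.5 | yes | yes |
| 12 | yes | yes |

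The rules disagree for every value from 1.05 up to, but not including, 10.5 g/dL. Women in that range meet criterion i and are ineligible under Section 1.4.2.

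**Step 3: is it an artefact of the text?**

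All four statements are in current body text, not in the summary of changes. The g/L unit appears in the same form in two separate places, and g/dL appears in two others. A fault in reading the PDF is therefore unlikely.

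**Step 4: does any analysis use the threshold?**

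Haemoglobin is not among the endpoints in Section 2.3. It is not among the criteria for moving into Part 2, and it plays no part in the sample-size reasoning in Section 8.1. It is not named among the exclusions from the Primary Evaluable Population in protocol Section 8.2.3 or SAP Section 3.3. Its only statistical footprint is the tabulation of entry violations.

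**The case against.** The strongest reply is that the protocol as a whole still excludes this anaemia. Section 3.14.3.1 makes the g/dL threshold a condition of enrolment before injection, and Section 1.4.2 repeats it. Section 1.4.1 makes the purpose of criterion i plain, and a literal cut-off of 1.05 g/dL is implausible, so this looks like a unit slip. A woman passed at screening on the g/L reading would still fail at Day 0. The likely cost is unnecessary pretreatment visits or confusion at a site. Criterion d (good general health) and exclusion z (investigator's judgement) give further protection. All of this stands, and it is why the severity is low.

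Three stronger readings are tempting, and the documents do not support them.

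- A reader might infer that anaemic women would be dosed, or were. The Day 0 condition stands in the way, and nothing in the documents shows that such a woman was enrolled.
- A reader might infer that Section 4.1 is the binding text and overrides Section 3.14.3.1. Section 4 bars waivers of eligibility criteria, but no passage ranks one section above the other.
- A reader might infer that a woman below 10.5 g/dL would escape being counted as a violation because she meets criterion i. Section 10.1.2 defines a violation as any departure from the protocol with a significant effect on subject safety or scientific value, and it gives entry criteria only as one example. Enrolling her would depart from Section 3.14.3.1 whatever Section 4.1 prints. What remains uncertain is how the event would be classified, because the two texts give different answers.

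It is also fair to say that little enrolment lay ahead. The amendment history records 12 subjects enrolled at Amendment 04, and the SAP (footnote to Section 1.2.1, and Section 13.3) records that Part 2 was never implemented. That left the optional third group of 6 and any expansion under Section 3.7. This reduces the value of an amendment but leaves the contradiction in the text.

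**Conclusion.** Wrong as written, low severity. Criterion i in the synopsis and Section 4.1 contradicts Sections 1.4.2 and 3.14.3.1 by a factor of 10 (1.05 against 10.5 g/dL). Read by itself, the one criterion that Section 1.4.1 relies on for anaemia does not do that job. The Day 0 condition contains most of the practical risk. Conflicting thresholds remain for the decision at the end of screening and for classifying entry violations.

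The range from 1.05 to 10.5 g/dL describes where the rules disagree. It does not measure how many women were exposed. The conclusion rests on the printed units and the standard conversion. It takes no position on which threshold is clinically right, and it does not affect any endpoint, sample size or planned analysis.

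**What to change.** Reconcile criterion i in the synopsis and in Section 4.1 with Section 1.4.2 (Menstrual Changes) and Section 3.14.3.1, so that one value and one unit stand in all four places. The sponsor must decide which value and unit those are.

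If enrolment is closed, an amendment adds little. In that case the clinical study report should state which haemoglobin threshold the sites applied and which was used to judge violations of entry criteria.

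The cost is a short text correction or one sentence in the report. Neither changes the design, the data collected or the analysis.

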# 4.2. Subject Exclusion Criteria

Subjects will be excluded from participating in this study if they meet any of the following criteria:

- a. has hypertension:
  - systolic BP  $\geq$ 160 mm Hg or diastolic BP  $\geq$ 100 mm Hg
  - vascular disease
- b. has current or history of ischemic heart disease
- c. has history of stroke
- d. has history of thromboembolic event
- e. has systemic lupus erythematosus
  - positive (or unknown) antiphospholipid antibodies
  - severe thrombocytopenia

- f. has rheumatoid arthritis on immunosuppressive therapy
- g. has migraine with aura
- h. has unexplained vaginal bleeding
- i. has diabetes
- j. has strong family history of breast cancer (defined as one or more first degree relatives, breast cancer occurring before menopause in three or more family members, regardless of degree of relationship, and any male family member with breast cancer), or current or history of breast cancer, or undiagnosed mass detected by breast exam
- k. has current or history of cervical cancer
- 1. has severe cirrhosis (decompensated) or liver tumors
- m. has one or more baseline liver function test(s) outside the local laboratory's normal range (Part 2 only)
- n. has known significant renal disease
- o. history of diagnosed clinical depression or bipolar disorder, with or without suicidal ideation, and/or history of suicide attempt
- p. in last 2 years, history of either hospitalization or medication management for psychiatric disorder that in the opinion of the investigator would make study participation unsafe, would interfere with adherence to study requirements or complicate data interpretation
- q. used DMPA products (Depo-Provera CI or Depo-subQ Provera 104) in the past 12 months
- r. used any of the following medications within 1 month prior to enrollment:
  - $\circ$  any investigational drug
  - prohibited drugs per protocol
  - oral contraceptives, contraceptive ring or patch
  - levonorgestrel intrauterine system (LNG IUS) or contraceptive implant
- s. used a combined injectable contraceptive in the past 6 months
- t. less than 3 months since the end of last pregnancy
- u. currently lactating
- v. is using or plans to use prohibited drugs per protocol in the next 18 months
- w. has known sensitivity to MPA or inactive ingredient
- x. has a plan to move to another location in the next 24 months
- y. in the opinion of the investigator, potentially at elevated risk of HIV infection (eg, HIV-positive partner, IV drug use by self or by partner)

z. has any condition (social or medical), which in the opinion of the investigator would make study participation unsafe, would interfere with adherence to the clinical study requirements or complicate data interpretation

# 4.3. Justification for Key Inclusion and Exclusion Criteria

Due to uncertain risk of pregnancy, all necessary precautions will be taken to minimize the risk of pregnancy among study subjects. Therefore, only women who are not pregnant, not wanting to become pregnant in the next 36 months, and who are at low risk of pregnancy will be enrolled in the study. The study will recruit women of reproductive age with regulatory menstrual cycle and with confirmed ovulation to ensure that the lack of ovulation during the treatment can be attributed to the treatment effect rather than the preexisting ovulatory dysfunction.

The study will not enroll female subjects who have medical contraindications to DMPA nor medical or social conditions that may make study participation unsafe, interfere with drug absorption and metabolism, have a strong family history of breast cancer defined as one or more first degree relatives, breast cancer occurring before menopause in three or more family members, regardless of degree of relationship and any male family member with breast cancer or complicate data interpretation.

# 4.4. Withdrawal Criteria and Procedures

In accordance with the Declaration of Helsinki (in accordance with the applicable country's acceptance), each subject is free to withdraw from the study at any time. The investigator also has the right to withdraw a subject from the study in the event of intercurrent illness, adverse events, pregnancy (see Section 7.2), or other reasons concerning the health or well-being of the subject, or in the event of lack of cooperation. In addition, a subject may be withdrawn from the study as described in Sections 3.12 and 7.1.7.

Should a subject decide to withdraw from the study, or should the investigator decide to withdraw the subject, every reasonable effort will be made to assess information relevant to the endpoints at the time of discontinuation. This may include but may not be limited to progesterone and MPA testing, pregnancy testing and assessment of ISRs, and/or acceptability. The final visit procedures should be followed for all subjects who withdraw, if possible (see Section 3.14.4.1).

The reason for and date of withdrawal from the study must be recorded on the source documentation and transcribed onto the CRF. If a subject withdraws consent, every attempt will be made to determine the reason. If the reason for withdrawal is an adverse event, monitoring will be continued at the discretion of the investigator (eg, until the event has resolved or stabilized, until the subject is referred to the care of a healthcare professional, or until a determination of a cause unrelated to the study drug or study procedure is made). The specific event or test result must be recorded on the source documentation and transcribed onto the CRF.

In addition, a blood sample will be obtained for the measurement of study drug concentration. The sample date and time will be recorded on the source documentation and transcribed to the CRF.

All assessments should be performed according to the protocol as soon as possible.

Since this is a single-dose study and the study product remains in the body months after injection, prompt withdrawal from the study treatment is not possible, and discontinuation from the study will not be the same as withdrawal from treatment. Study staff will explain to subjects who wish to discontinue from the study early that it is impossible to discontinue the treatment and that it is important to stay in the study at least until safety assessments are completed (including delayed return to ovulation [>12 months post-study drug injection]).

# 5. TREATMENT OF SUBJECTS

# 5.1. Drugs Administered During the Study

In Part 1 of the study after enrollment, 12 enrolled subjects will be sequentially assigned to a treatment group as presented below.

The first 6 subjects will be assigned to:

• Treatment group 1: 0.3 mL of 400 mg/mL of undiluted TV-46046 (120 mg)

The next 6 subjects will be assigned to:

• Treatment group 2: 0.6 mL of 200 mg/mL of saline-diluted TV-46046 (120 mg)

If warranted, an additional 6 subjects in Part 1 will be assigned to:

• Treatment group 3: 0.4 mL of 300 mg/mL of saline-diluted TV-46046 (120 mg)

In Part 2 of the study, subjects will be randomly assigned to 1 of up to 3 treatment groups (up to 3 additional dose levels of undiluted TV-46046 within the range of 80 to 300 mg).

### 5.1.1. Dilution Procedure of TV-46046

Diluted TV-46046 will be prepared by the investigational center pharmacist or other trained personnel. Dilution procedures for TV-46046 treatment group 2 in Part 1 and, potentially, treatment group 3 in Part 1, are provided in the Pharmacy Manual.

### 5.1.2. Subcutaneous Administration of TV-46046

In both parts of the study TV-46046 will be administered by a study staff member as a single subcutaneous injection in the abdomen during the first 5 days of the menstrual cycle using a 23 gauge 3/8 inch needle following the sponsor's instructions for administering a subcutaneous injection (see Appendix B).

Part 2 will be a subject-blinded study. The clinical staff providing the injections will be trained to shield the syringe from view of the subject or any other study staff prior to and at the time of injection. For additional details, see Section 3.8.2.

Briefly, the provider will follow these steps:

- 1. Use alcohol pad to wipe the skin in the abdominal injection area and allow the skin to dry
- 2. Gently grasp and squeeze a large area of skin in the chosen injection area between the thumb and forefinger, pulling it away from the body
- 3. Insert the 23 gauge 3/8 inch needle at a 45° angle so that most of the needle is in the fatty tissue

- 4. Inject the medication slowly (over 5 to 7 seconds) until the syringe is completely empty
- 5. After withdrawing the needle, press a cotton pad lightly on the injection area (do not use Band-Aid®4 taking care of not rubbing the site of injection

# 5.2. Restrictions

Medications prohibited before and/or during the study are described in Section 5.3. Subjects will remain at the investigational center for at least 15 minutes after the study drug injection for observation. The investigational center will have an EpiPen (epinephrine injection) available and easy access to emergency care necessary in the unlikely event of anaphylaxis or anaphylactoid reaction.

# 5.3. Prior and Concomitant Medication or Treatment

Any prior or concomitant therapy, medication, or procedure a subject has had within 30 days before study drug administration and up to the final visit will be recorded on the CRF. During the scheduled follow-up visits, the investigator will ask subjects whether they have taken any medications (other than study drug), including over the counter (OTC) medications, vitamins, or herbal or nutritional supplements, since the previous visit. During laboratory visits information of the use of concomitant medications will be documented only if reported by the subject. Generic or trade name, indication, route of study drug administration, dosage, and start and end dates will be recorded.

Any drugs that may interfere with metabolism of MPA or affect ovarian function will be prohibited during the study. The following medications should not be used during this study (unless medically indicated):

- rifampicin
- griseofulvin
- anticonvulsants
- barbiturates
- antiretroviral drugs (ARVs): non-nucleoside reverse transcriptase inhibitors (efavirenz, nevirapine) and ritonavir-boosted protease inhibitors
- aminoglutethimide
- St. John's wort
- selective cyclooxygenase-2 (COX-2) inhibitors (eg, meloxicam, celecoxib) for 5 or more consecutive days
- steroids (synthetic estrogens, progestins, androgens)

<sup>4 Band-Aid is a registered trademark of Johnson & Johnson Corporation.

